To the best of our knowledge, there is no research on the effects of IV lignocaine infusion on intraoperative desflurane requirements in human population. Reduction of desflurane requirements when coupled with the reported benefits of IV lignocaine, will contribute to a high quality, cost effective, optimal, balanced and safe provision of anaesthesia.

OBJECTIVE

1. To investigate the effect of IV lignocaine on the end tidal desflurane concentration required to maintain BIS values between 40-60.
2. To compare intraoperative haemodynamic changes in patient with intravenous lignocaine vs normal saline.

MATERIALS AND METHODS

This prospective, double-blinded, randomised controlled study will be submitted for the approval of the Research Committee of Department of Anaesthesiology & Intensive Care, Universiti Kebangsaan Malaysia Medical Centre (UKMMC), Research & Ethics Committee, UKMMC and will be registered at ClinicalTrials.gov.

Written informed consent will be obtained from selected patients recruited into the study, which will be conducted by a single operator who is the principal investigator of this study. The study will be conducted in Hospital Universiti Kebangsaan Malaysia, Kuala Lumpur.

Inclusion Criteria:

1. American Society of Anaesthesiology (ASA) I or II patients.
2. Patients aged between 18-75 years of age.
3. Patients scheduled for elective laparoscopic cholecystectomy.
4. Patients scheduled for laparoscopic hernioplasty.
5. Patients scheduled for emergency laparoscopic appendicectomy.
6. Patients scheduled for emergency laparoscopic cystectomy.
7. Patient weight ranging from 50 – 100 kg.
8. Surgery lasting at least one hour.

Exclusion Criteria:

1. Patients with a known allergy to study drug.
2. Patients with body mass index (BMI) more than 35 kg m⁻².
3. Patients who are taking sedatives.

4. Patients with chronic substance abuse.
5. Patients with history of seizures, psychiatric disorders, cardiac failure, arrhythmias, hepatic or renal dysfunction.
6. Patients who are taking class IB antiarrhythmics or amiodarone.
7. Surgery lasting more than 3 hours.

Methodology:

Patient will be reviewed and recruited during premedication round, written consent will be explained and obtained. Patients will be fasted for at least six hours before their surgery. Tablet paracetamol 1g will be given to patients once they are called to operation theatre.

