Anaesthesia will be induced with IV fentanyl 2 mcg kg⁻¹ followed by IV propofol 2-3 mg kg⁻¹ and IV rocuronium 0.6 mg kg⁻¹. After 3 minutes of mask ventilation with only 100% oxygen, tracheal intubation using an appropriately sized endotracheal tube (ETT) will be performed to secure patient's airway. The patient will then be connected to Aisys CS² anaesthesia machine and the lungs will be ventilated with desflurane in 50% oxygen-air balance at a tidal volume of 6-8 ml kg⁻¹. End tidal CO₂ (EtCO₂) level will be maintained between 35-45 by adjusting the respiratory rate. The time of induction and intubation will be documented.

Anaesthesia shall be maintained with desflurane, in 50% oxygen-air balance with a total flow of 1.0 L min⁻¹. The end tidal desflurane (Et-Des) concentration will be adjusted to maintain a target BIS of between 40-60. BIS, MAC values, Et-Des concentration, BP and HR will be recorded every 10 min from the time of induction until the end of surgery. IV parecoxib 40 mg will be given to all patients. Boluses of IV fentanyl 50 mcg will also be given to maintain blood pressures within 20% of pre-operative levels. Dosage of fentanyl given post induction will be recorded. Bolus of IV ephedrine 6 mg will be given during hypotensive episodes with HR less than 60 beat per min while those with normal HR will be given a bolus of IV phenylephrine 100 mcg. Patients will also be given IV dexamethasone 8 mg post induction and IV granisetron 1 mg 30 mins before end of surgery to reduce the risk of post-operative nausea and vomiting. Core temperatures will be maintained above 35 °C with fluid warmer and warming blanket. If surgery lasts more than 3 hours, patient will be excluded from the study and infusion of the study drug will be stopped.

Desflurane and study infusions will be discontinued and estimation of desflurane cost will be estimated at the end of surgery. Neuromuscular block will be reversed with a combination of IV atropine 1 mg and IV neostigmine 2.5 mg. When the patient meets all criteria for extubation, the ETT will be removed. Time to extubation (defined as time from desflurane discontinuation to tracheal extubation) will be recorded. Pain score will be assessed in recovery bay and if required, patient will be given patient-controlled analgesia morphine.

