Signs of lignocaine toxicity will be monitored in all patients beginning from the time of bolus of the study drug until one-hour post operatively in the recovery bay. During general anaesthesia, signs of lignocaine toxicity that will be looked out for include an initial tachycardia and hypertension followed by prolonged PR interval, widened QRS, sinus bradycardia, ventricular arrhythmias, hypotension and cardiac arrest. When the patient is awake in recovery bay, along with late signs of lignocaine toxicity as mentioned above, patient will be observed for one hour for early signs and symptoms characterised by perioral numbness, tinnitus, light headedness, visual disturbances, muscle twitching, seizure, altered mental state and respiratory arrest. If any of these were to occur, then infusion of the study drug will be stopped and these patients will be excluded from the study and managed according to hospital protocol.

STATISCAL ANALYSIS

a) Sample size calculation:

The α value is set at 0.01 and power of study at 90%. The sample size is calculated using t- test. Calculation as derived from a study by Kuo et al (2006) and Omar et al (2019).^{6, 12}

The sample size is calculated using the “Power and Sample Size Calculations” program.

Sample size was calculated using t-test.

Requested output: Sample size

Design: Independent

Input: $\alpha = 0.01$; power = 0.9; $\delta = 0.5$; $\sigma = 0.4$; $M = 1$

[figure not shown]
Case sample size: 21 x 2 plus 10% drop out rate = 48

Sample = 24 per study group

b) Statistical test:

Analysis will be analysed using SPSS software for windows. The Kolmogorov-Smirnov test will be used to assess variable normality distribution. Categorical variables will be analysed by chi square test. Continuous variables will be compared using student's t -test. p value less than 0.05 will be regarded as statistically significant.

FLOW CHART

AAGBI Safety Guidelines

Management of Severe Local Anaesthetic Toxicity

1 Recognition	Signs of severe toxicity: 
 Sudden alteration in mental state, severe agitation or loss of consciousness, with or without tonic-clonic convulsions Cardiovascular collapse: sinus bradycardia, conduction blocks, asystole and ventricular tachyarrhythmias may occur Local anaesthetic (LA) toxicity may occur some time after an initial injection 	

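### The trial is sized at alpha 0.01 but judged at p < 0.05, and no per-patient end-tidal desflurane value is named for the t-test

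*Combined protocol and SAP*

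**What the plan says.** The combined document makes two statements about significance, both in its statistical analysis section.

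- Part a), sample size: "The α value is set at 0.01 and power of study at 90" per cent. The program inputs repeat alpha 0.01 and give delta 0.5, sigma 0.4 and a 1:1 ratio under "Design: Independent". The result is "Case sample size: 21 x 2 plus 10% drop out rate = 48", or 24 per group.
- Part b), statistical test: "p value less than 0.05 will be regarded as statistically significant". No outcome is exempted.

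The method for continuous data is one sentence: "Continuous variables will be compared using student's t -test".

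The first objective is "To investigate the effect of IV lignocaine on the end tidal desflurane concentration required to maintain BIS values between 40-60". Et-Des is also the outcome in the title, although the document labels no outcome as primary. Under Methodology, "BIS, MAC values, Et-Des concentration, BP and HR will be recorded every 10 min from the time of induction until the end of surgery". The data collection sheet has an Et-Des row with columns from 0 to 190 minutes, and its footnote marks column 0 as taken before induction.

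**The concern.** The sample size section tells a reader that the Et-Des comparison runs a 1% risk of a false positive and has 90% power. The test section applies a 5% rule. Only one of these can govern the result, and the document does not explain the difference. A report that quoted the design alpha and power next to a conclusion drawn at 0.05 would misdescribe the test.

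The second gap concerns the same test. A two-sample t-test needs one number per patient. Each patient will have a series of Et-Des readings, and no rule reduces the series to one number. Two analysts following the text could use the mean over the whole operation, the mean over a fixed window, or the reading at one time. Because operations differ in length, these are different quantities. The text also does not say whether the pre-induction column is left out, or which of these quantities delta 0.5 and sigma 0.4 describe.

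**Working it through.** **Inputs.** From part a) of the statistical analysis section: alpha 0.01, power 0.90, delta 0.5, sigma 0.4, ratio 1:1, dropout 10%. From part b): threshold 0.05. Sidedness is not stated.

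**Formula.** Two-sample t-test with n per group, df = 2n − 2, noncentrality = (delta/sigma)·√(n/2). Two-sided power is P(|T| > t(1 − alpha/2, df)) for T noncentral t.

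**Step 1: reproduce the plan's figure.** For n = 21, df = 40 and the noncentrality is (0.5/0.4)·√10.5 = 4.05. At two-sided 0.01 the critical value is 2.704.

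- n = 20: power 88.5%
- n = 21: power 90.4%

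So 21 is the smallest group size that reaches 90%, which matches the plan. A one-sided 0.01 test would need 19. Dropout: 21/0.9 = 23.3, rounded up to 24 per group, 48 in all. Alpha 0.01 was really used and is not a misprint of 0.05.

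**Step 2: the same design under the 0.05 rule.**

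| n per group | Power at 0.01 | Power at 0.05 |
|---|---|---|
| 15 | 74.0% | 91.1% |
| 21 | 90.4% | 97.7% |
| 24 | 94.5% | 98.9% |

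At 0.05, 14 per group gives 88.9%, so 15 is the smallest size that reaches 90%.

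**Step 3: where the two rules disagree.** With 21 per group and SD 0.4, the standard error is 0.4·√(2/21) = 0.1234.

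- p = 0.05 at a difference of 2.021 × 0.1234 = 0.249
- p = 0.01 at a difference of 2.704 × 0.1234 = 0.334

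A difference between these is significant at 0.05 but not at the design alpha. The chance of landing there is the difference between the two rejection probabilities:

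- no true effect: 5% − 1% = 4%
- true difference 0.5: 97.7% − 90.4% = 7.3%

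With 24 per group the band is 0.232 to 0.310, and the second probability is 98.9% − 94.5% = 4.4%.

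**Step 4: the value tested.** Eligible operations last 1 to 3 hours. At one reading per 10 minutes that is about 60/10 = 6 to 180/10 = 18 readings after induction. The sample size is that of one comparison of one value per patient. Neither part of the statistical analysis section says which value. Stated power depends on whether 0.4 is the SD of the value tested. With delta 0.5 and 21 per group:

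| SD of the tested value | Power at 0.01 | Power at 0.05 |
|---|---|---|
| 0.3 | 99.5% | over 99.9% |
| 0.4 | 90.4% | 97.7% |
| 0.5 | 70.2% | 88.5% |
| 0.6 | 50.5% | 75.0% |

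The SDs other than 0.4 are assumed, to show the range.

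**The case against.** The strongest reply on alpha is that the document contains only one decision rule. Alpha 0.01 appears only as a planning input, and a trial may be sized more strictly than it is tested. Read literally, p = 0.03 is significant. Sizing at 0.01 and testing at 0.05 keeps the test at its nominal 5% and raises power. All of this stands. What it leaves is a stated alpha and power that belong to a different test, with nothing to say that this was intended.

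On the unnamed value, the reply is that a patient mean is the natural choice, and that the cited studies or the program output, which is not shown here, may make clear what delta and sigma measure. That may settle the meaning of sigma. It would not put a rule into part b), where the value should be named and the text is plain and complete.

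Three stronger readings are tempting, and the documents do not support them.

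- *The trial is underpowered.* The mismatch works the other way: 97.7% against 90.4%. Low power would follow only if the tested value had an SD well above 0.4, and nothing in the documents shows that.
- *The false-positive rate is out of control.* A single test at 0.05 has a 5% rate. That is five times the design alpha, but it is still a valid 5% test.
- *Et-Des will be tested at every 10-minute reading.* The plan does not say so, and a sample size built on one delta for two independent groups points to one comparison.

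**Conclusion.** The concern holds in limited form. The clear error is the mismatch: the stated alpha of 0.01 and power of 90% do not describe the rule of p < 0.05. Its size is a band of observed differences from about 0.25 to 0.33 where the two thresholds disagree, reached with probability 4% under no effect and 7% at the planned difference (21 per group, SD 0.4, normal data, two-sided test).

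The missing definition of the per-patient Et-Des value is real but closer to missing detail. Its effect on power cannot be fixed from the documents, because they give neither the correlation between readings nor the quantity to which sigma 0.4 belongs. Treating Et-Des as the main outcome is an inference from the title and the first objective.

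**What to change.** Before unblinding, amend the statistical analysis section in two places.

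1. **One alpha.** State the same two-sided alpha for the Et-Des comparison in parts a) and b). Either keep 0.01, in which case the 90% power stands (90.4% with 21 per group), or choose 0.05 and restate the power as 97.7% with 21 per group. Enrolment stays at 24 per group either way.
2. **One value.** Name the per-patient Et-Des value. One form would be the mean of the readings after induction over a window fixed in advance, leaving out the pre-induction column and tested once between groups. Say that delta 0.5 and sigma 0.4 refer to that value, with units and source. If this cannot be shown, replace the single power figure with the range of SDs in the second table above.

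A sensitivity analysis restricted to readings with BIS between 40 and 60 would suit the wording of the first objective, but it is optional.

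The cost is a few sentences, with no extra patients or data. Readings outside the window would not enter the main test, and choosing 0.01 gives up some power (90.4% against 97.7%).

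### Objective 2 has no pre-specified haemodynamic summary and no multiplicity control: t-testing BP and HR at each 10-min reading would give roughly a 25% to 85% chance of a false difference

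*Combined protocol and SAP*

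**What the plan says.** The second objective is "To compare intraoperative haemodynamic changes in patient with intravenous lignocaine vs normal saline". It names no variable, time point or summary.

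Under Methodology, "BIS, MAC values, Et-Des concentration, BP and HR will be recorded every 10 min from the time of induction until the end of surgery". BP and HR are also taken before induction and after the study-drug bolus. The inclusion criteria require "Surgery lasting at least one hour", and at the other end "If surgery lasts more than 3 hours, patient will be excluded from the study and infusion of the study drug will be stopped". A retained patient therefore contributes about 6 to 18 readings after induction. The data collection sheet has 19 columns after time 0, and each BP entry is two numbers.

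The statistical section, part b (Statistical test), treats all continuous variables alike: "Continuous variables will be compared using student's t -test. p value less than 0.05 will be regarded as statistically significant". It gives no repeated-measures method, no reduction to one value per patient and no multiplicity rule.

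**The concern.** A two-sample t-test compares one number per patient. Objective 2 produces a series per patient for at least two variables, and the plan does not say how the series becomes one number. The two most direct ways of applying the stated test are both faulty:

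- **A test at each time point** gives many chances of p < 0.05 with no control of the overall error. Columns after 60 min compare only patients still in surgery, so late results rest on few, selected cases.
- **All readings pooled in one test** treats repeated readings of one patient as independent and overstates the information.

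Haemodynamics is one of only two objectives, and the Introduction presents a more favourable cardiovascular profile as an expected benefit. An isolated low p-value could be reported as support for that. Because the choice is not written down, it can be made after the data are seen.

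**Working it through.** **Inputs from the documents.** 24 patients per group, 0.05 per test, readings every 10 min, surgery from 1 to 3 h.

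**Assumed, because the documents give no value.** Correlation between readings of one patient, BP–HR correlation (0.2), and the distribution of durations.

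**The plan's own figure.** The plan states no error rate for Objective 2. Its sample size does reproduce. A two-sided t-test with alpha 0.01, power 0.90 and δ/σ = 0.5/0.4 = 1.25 needs 21 per group (power 0.904; 20 gives 0.885). With 10% dropout, 21/0.9 = 23.3, so 24 per group and 48 in total.

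**Step 1: number of tests.** With BP counted as one variable, there are 2 × 6 = 12 tests at 1 h and 2 × 18 = 36 at 3 h.

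**Step 2: one test per reading.** For k independent tests, P(at least one p < 0.05) = 1 − 0.95^k. For k = 12 this is 1 − 0.540 = 46.0%. For k = 36 it is 1 − 0.158 = 84.2%. Readings 10 min apart in one patient are correlated, which lowers the figure. The correlated columns are simulated under no effect, 24 per group, with every patient observed to the stated duration:

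| Duration | Tests | Independent | AR(1) 0.5 | AR(1) 0.7 | AR(1) 0.9 | Exchangeable 0.5 | Exchangeable 0.7 |
|---|---|---|---|---|---|---|---|
| 1 h | 12 | 46.0% | 42% | 36% | 24% | 37% | 30% |
| 90 min | 18 | 60.3% | 55% | 48% | 33% | 48% | 38% |
| 2 h | 24 | 70.8% | 65% | 56% | 38% | 55% | 42% |
| 3 h | 36 | 84.2% | 79% | 70% | 50% | 65% | 48% |

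The range is about 24% to 85%. The top needs independent readings and every case lasting 3 h; the bottom needs strong correlation and every case lasting 1 h. If systolic and diastolic pressure are tested separately (assumed correlation 0.7), AR(1) 0.7 gives 45% at 1 h and 81% at 3 h.

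**Step 3: varying durations.** These runs use a patient-level correlation of 0.3 to 0.6 plus AR(1) of 0.6 to 0.8, and two variables. Durations uniform on 60 to 180 min give about 31 tests and 49% to 66%. Durations uniform on 60 to 120 min give about 21 tests and 39% to 53%. The first 60 min alone gives 23% to 34%.

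**Step 4: late columns.** With durations uniform on 60 to 180 min, the number per group still in surgery at 150 min is 24 × (180 − 150)/(180 − 60) = 6.

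**Step 5: pooled readings.** With m readings per patient and common correlation ρ, the true variance of the difference is about 1 + (m − 1)ρ times what the t-test assumes. For m = 12 and ρ = 0.5 this is 1 + 11 × 0.5 = 6.5. The false-positive rate is then 2 × [1 − Φ(1.96/√6.5)] = 2 × [1 − Φ(0.769)] = 44%. For ρ = 0.3 the factor is 4.3 and the rate 34%; for ρ = 0.7 they are 8.7 and 51%. Simulation with the Step 3 settings gives 37% to 54% for one variable.

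**Step 6: one mean per patient.** A t-test of each patient's mean over the first 60 min, two variables at 0.025 each, gives about 5.0% under the Step 3 correlations.

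**The case against.** The main objection is that the plan never commits to a test at each reading. The collection sheet is a recording form, not an analysis schedule, and a t-test of one mean per patient fits the stated wording and is valid. This stands: the defect is an unspecified analysis, and the error rates are conditional on how the gap is filled. It does not remove the point, because the valid option is not written down and neither its variable nor its window is fixed.

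A reader might infer that a false haemodynamic finding is more likely than not. The documents do not support that. It requires per-reading testing and then, with independent tests, at least 14 of them (1 − 0.95^14 = 51.2%). With shorter operations or strong correlation the figure falls below 50%, and the documents give neither a duration distribution nor a correlation. The three-variable figures also assume that systolic and diastolic pressure are analysed separately, which is not stated.

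Parts of the remedy are also a matter of choice. Holm is one option among several. A 60-min window takes later readings out of the formal test although the infusion runs to the end of surgery. Finally, this objective is listed second, and the end-tidal desflurane comparison is unaffected.

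**Conclusion.** The point holds in conditional form. Nothing in the plan fixes the haemodynamic summary or limits the number of tests, and this is more than missing detail, because both direct applications of the stated t-test inflate false positives several-fold. Per-reading testing of BP and HR gives roughly 25% to 85%; even the low end is about five times the nominal 5%. Pooling gives roughly 40% to 50% for one variable. These figures rest on assumed correlations and durations and, for the first, on the inference that tests are run at each reading. The recommendation does not depend on the chance exceeding one half.

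**What to change.** In part b of the statistical section, name one comparison for each of mean arterial pressure (with its derivation from the two recorded BP values) and HR. This is the difference between groups in the per-patient mean over a window that every eligible patient reaches, such as the first 60 min after induction. Use a t-test of those means, or a mixed model with patient as random effect.

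Judge the two tests together at 0.05, for example by Holm, or label Objective 2 exploratory. Show time-point differences, including later readings, as plots with confidence intervals, the number of patients at each time and no significance claims.

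The cost is a few sentences and a routine SPSS analysis of data already being collected, with no added patients. The downside is that isolated time-point p-values can no longer be claimed and readings after the window become descriptive.

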1. DEMOGRAPHIC DATA

Age	
Gender	Male/ Female
ASA	I/ II
Weight (kg)	
Height (m)	
Past medical illness (if any state current medications)	
Diagnosis	
Surgical Procedure	

